### **SECONDARY OUTCOMES:**

- ***Preeclampsia:*** characterized by hypertension and proteinuria occurring after the 20th week of pregnancy. Hypertension is a blood pressure of 140/90 mm Hg or above. In severe pre-eclampsia the diastolic blood pressure is usually 110 mm Hg or above and there may also be one or more of the following symptoms: severe headache, blurred vision, nausea and/or vomiting, abdominal pain and a diminished urinary output, i.e., oliguria. ***Early onset Preeclampsia*** develops before 34 weeks of gestation.
- ***Eclampsia:*** Very serious complication of pregnancy characterized by convulsions and coma. It may be preceded by signs of pre-eclampsia or the onset may be rapid and sudden. Eclamptic fits can occur in pregnancy, labour or soon after delivery.
- ***Small for gestational age:*** newborns with weights below the 10th percentile for gestational age.
- ***Perinatal mortality:*** The number of stillbirths and deaths in the first week of life per 1,000 live births, the perinatal period commences at 22 completed weeks (154 days) of gestation and ends seven completed days after birth.

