### **FETAL OUTCOMES OF INTEREST**

- ***Preterm birth <34 0/7 weeks of pregnancy:*** live birth before 34 0/7 weeks of pregnancy are completed.

- **Birth weight <2500g and Birth weight <1500g:** Birth weight is defined as the first weight of the fetus or newborn obtained after birth. For live births, birth weight should preferably be measured within the first hour of life before significant postnatal weight loss has occurred, recorded to the degree of accuracy to which it is measured (WHO). Birth weight <2500 g is defined as low birth weight, whereas birth weight <1500 g is defined as very low birth weight.
- **Fetal Loss:** Spontaneous loss  $\geq$  16 weeks GA plus perinatal mortality.
- **Late abortion:** Spontaneous fetal loss  $\geq$  16 weeks.
- **Spontaneous abortion:** Premature expulsion of a non-viable fetus from the uterus at  $<$  20 weeks gestation.
- **Stillbirth:** Birth of a baby that shows no signs of life at birth (no gasping, breathing, heart beat or movement). (WHO). It may be a macerated or fresh stillbirth. The signs of maceration are discoloration and peeling of the skin leaving areas of raw tissue. The skull is usually soft, as the brain has become soft. The umbilical cord is usually stained a dark red or black. The amniotic fluid is usually darkly stained. Maceration is the result of the infant being dead for at least 12 hours. Macerated stillborn infants are assumed to have died before the onset of labor. Fresh stillbirths show no sign of maceration and have usually died during labor or shortly before the onset of labor.
- **Medical termination of pregnancy:** an operation or other procedure to terminate pregnancy before the fetus is viable.

**NOTE:** (WHO) at the end of the definition means the definition is from the 2006 WHO guide titled: *Integrated Management of Pregnancy and Childbirth Pregnancy, Childbirth, Postpartum and Newborn Care: A guide for essential practice.*

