#### **3.2 Secondary Hypotheses and Associated Outcomes**

The study will also test three secondary hypotheses:

- Infants of women who take antenatal daily LDA initiated at 6 0/7 to 13 6/7 weeks GA will be at lower risk of being small for gestational age (SGA).
- Women who take antenatal daily LDA initiated at 6 0/7 to 13 6/7 weeks GA will have lower risk of: eclampsia and preeclampsia. Note that this hypothesis will be operationalized as evidence of hypertensive disorders of pregnancy as defined in more detail in Sections 9 and 12.
- Infants of women who take antenatal daily LDA initiated at 6 0/7 to 13 6/7 weeks GA will be at lower risk of perinatal mortality.

These secondary hypotheses will be tested using the following outcomes.

- Small for gestational age infants include newborns with weights below the 10th percentile for gestational age, as defined by Intergrowth Standards.
- Risk of Pregnancy Induced Hypertension (eclampsia and/or preeclampsia) defined as a binary outcome of any of new onset hypertension that occurs beyond 20 weeks gestational age, preeclampsia, or eclampsia happening between initiation of study dosing and participant completion of the study at 6 weeks after delivery. Eclampsia is a serious complication of pregnancy characterized by convulsions and coma. It may be preceded by signs of pre-eclampsia or the onset may be rapid and sudden and can occur in pregnancy, labor or soon after delivery. Preeclampsia is characterized by hypertension and proteinuria occurring after the 20th week of pregnancy. See Sections 9 and 12 for more detail.

- Perinatal mortality is a binary outcome that includes any stillbirth occurring after 20 weeks pregnancy and any early neonatal death that occurs within 7 days after delivery.

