Small for Gestational Age	Binary	
The unit of analysis is the infant delivered from each individual pregnancy. The outcome will be classified as “Yes” if the infant is classified as SGA, defined as a newborn with weight below the 10th percentile for gestational age” and “No” otherwise. Note that growth curves appropriate for each GN site based on Intergrowth standards will be used to define the expected gestational age distribution.
 
For any outcomes involving birth weight, the reported weight will only be used to calculate that outcome if collected within 4 days of birth. Any weight captured after 4 days will be excluded.
 
Analysis Population: mITT

Perinatal Mortality	Binary	
The unit of analysis is the infant delivered from each individual pregnancy. The outcome will be classified as “Yes” if the infant is a fresh or macerated stillbirth or a death in the first week of life; the perinatal period commences at 20 completed weeks (154 days) of gestation and ends seven completed days after birth. Pregnancies terminated prior to 20 completed weeks of gestation will be treated as missing for this outcome.
 
Analysis Population: mITT

Variable	Type	Definition
Other Outcomes of Interest—Maternal Outcomes		
Preterm, preeclampsia	Binary	
The unit of analysis is the woman randomized to the trial who delivers after 20 weeks gestational age. The outcome will be defined as delivered at less than 34 weeks GA AND also meeting the criteria for the endpoint “Preeclampsia and eclampsia (or more appropriately hypertensive disorders of pregnancy).”
 
Analysis population: mITT

Vaginal Bleeding	Binary	
The unit of analysis will be individual woman. Per the protocol, Vaginal Bleeding is defined as: “Bleeding during pregnancy (i.e., WHO generally defines as ‘light’ or ‘heavy’ bleeding based on clinical symptoms).” This outcome will be defined based on Question 2e of Form ASP06 and will be classified as “Yes” if the response to this question is Yes at any bi-weekly visit, and No if all completed biweekly visits have either a No or a DK response. Any woman with at least one biweekly visit form will be included in the denominator; the outcome will be classified as missing if a subject has no biweekly visit forms.
 
Analysis population: ITT

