Late Abortion	Binary	
The unit of analysis will be individual woman. Per the protocol, late abortion is defined as: "Spontaneous fetal loss <math>\geq</math> 16 weeks." This outcome will be defined based on a response of 4 for Question A7 from Form MN02 from the MNH registry and will be classified as "Yes" if that response is listed as the Mode of Delivery and the pregnancy has a GA of 16 weeks or greater and "No" otherwise. Per the MNH Registry Manual of Operations, that mode of delivery should be used if "A delivery prior to 20 weeks gestation (or <500 g). Miscarriage is also known as spontaneous abortion." If the delivery is after 20 weeks and is classified as a miscarriage on the form, the outcome will be reclassified as a stillbirth. Individuals with loss prior to 16 weeks will be excluded from the analyses.
 
Analysis population: ITT

Variable	Type	Definition
Other Outcomes of Interest—Fetal Outcomes		
Preterm birth <34 0/7 weeks of pregnancy	Binary	
The unit of analysis will be the individual delivered fetus or infant (either live birth or stillbirth); note that per the protocol, the event is defined as: “live birth before 34 0/7 weeks of pregnancy are completed,” so this definition represents a departure from the protocol. This will be defined as a secondary variable in the analysis data set based on gestational age as determined from ASP forms and neonatal outcome as determined from Form MN02 from the MNH Registry.
 
Analysis population: mITT

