Fetal Loss	Binary	
The unit of analysis will be the individual delivered fetus or infant and per the protocol, the event of fetal loss is defined as: "Spontaneous loss <math>\geq</math> 16 weeks GA plus perinatal mortality." This binary outcome measure will be defined in the analysis data set based on gestational age as measured via the ASP forms and mortality outcomes as determined from Forms MN02 and MN03 from the MNH Registry. Any death of an infant greater than 16 weeks GA and prior to 7 days post-delivery will be classified as "Yes" and live births classified as alive at 7 days will be classified as "No." Any fetal loss (including MTP or miscarriage) that occurs prior to 16 weeks will be treated as a missing value.
 
Analysis population: ITT

Variable	Type	Definition
Spontaneous abortion	Binary	
The unit of analysis is the individual pregnancy. Per the protocol, the binary outcome of spontaneous abortion is defined as: "Premature expulsion of a non-viable fetus from the uterus at < 20 weeks gestation." This outcome will be defined based on Questions A7-4 or C1 from Form MN02 from the MNH registry and will be classified as "Yes" if the response to A7-4 is listed as the Mode of Delivery or the response to C1. Fetal/Neonatal outcome is answered 1. Miscarriage and "No" otherwise. Per the MNH Registry Manual of Operations, that mode of delivery should be used if "A delivery prior to 20 weeks gestation (or <500 g). Miscarriage is also known as spontaneous abortion."
 
Analysis population: ITT

Stillbirth	Binary	
The unit of analysis will be the individual infant that delivers at 20 weeks gestational age or greater during the specified analysis period. The event will be classified as "Yes" if the infant is classified as a non-macerated still birth or with maceration status unknown via Forms MN02 and MN05 in the MNH Registry and "No" if the baby is born alive as specified via Form MN02 in the MNH Registry. Note that infants classified as Macerated still births are not included in this population. Also note that deliveries classified as miscarriages but that have GA of 20 weeks or greater will be reclassified as stillbirths.
 
Analysis population: mITT

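### The SAP's stillbirth row leaves out macerated stillbirths without flagging it, and its perinatal-mortality row pairs 20 weeks with 154 days and lowers the protocol's 22-week threshold undeclared

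*Combined protocol and SAP*

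**What the plan says.** **Stillbirth.** Protocol Appendix 3 defines stillbirth as birth without signs of life and says of it: "It may be a macerated or fresh stillbirth". It takes macerated infants to have died before labour began. In SAP 9.2 the event is Yes for a stillbirth that is non-macerated or of unknown maceration status, and No for a live birth. The row then states: "Note that infants classified as Macerated still births are not included in this population". It also says that "deliveries classified as miscarriages but that have GA of 20 weeks or greater will be reclassified as stillbirths". Table 5a prints the result simply as Stillbirth.

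**Perinatal mortality.** Protocol Appendix 3 says that "the perinatal period commences at 22 completed weeks (154 days) of gestation and ends seven completed days after birth". SAP 9.2 says that "the perinatal period commences at 20 completed weeks (154 days) of gestation and ends seven completed days after birth", and continues: "Pregnancies terminated prior to 20 completed weeks of gestation will be treated as missing for this outcome". SAP 3.2 defines the outcome as "any stillbirth occurring after 20 weeks pregnancy and any early neonatal death that occurs within 7 days after delivery".

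**Declared changes.** SAP Section 12 names two outcome changes: preeclampsia/eclampsia is restated as hypertensive disorders of pregnancy, and preterm preeclampsia is added. Within SAP 9.2, the row for preterm birth before 34 weeks flags its own change: "so this definition represents a departure from the protocol". Neither the stillbirth row nor the perinatal-mortality row carries such a note.

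**The concern.** A macerated stillbirth is neither Yes nor No in the SAP row. It leaves both numerator and denominator because of something that happened after randomisation. What remains is an estimate for non-macerated stillbirth under the name of the protocol's broader outcome. A reader has little cue to notice: among the other outcomes of interest that have an Appendix 3 definition, stillbirth is the only one whose SAP row does not cite that definition.

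The omitted deaths matter to the trial's rationale. Protocol 1.3.1 places stillbirth among the consequences of placental dysfunction that aspirin might reduce, 2.11 cites a reduction in stillbirth as a benefit, and 2.8 lists stillbirth for fetal safety monitoring. An effect on deaths before labour, in either direction, would be largely invisible in this row. It is the only Table 5a row confined to fetal deaths at 20 weeks or later: perinatal mortality adds early neonatal deaths, and fetal loss also adds losses from 16 weeks.

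The reclassification rule adds a second difficulty. It does not say whether maceration is checked when a recorded miscarriage at 20 weeks or later becomes a stillbirth. The same death could count or drop out according to how the form was coded.

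For perinatal mortality, the week and day figures in one sentence disagree about deaths at 140 to 153 days. Whichever is used, readers would not learn from Section 12 that the protocol's threshold had moved.

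**Working it through.** **Threshold.** The SAP's figure for 20 completed weeks is 154 days.

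- 20 × 7 = 140 days, so the SAP's pair does not reproduce.
- 22 × 7 = 154 days, so the protocol's pair does.
- 154 − 140 = 14 days.

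SAP 3.2, the sentence that follows in the same row, and the mITT population (delivery at 20 weeks or later) all point to 20 weeks. The day count therefore looks like a leftover from the protocol text, and the event definition was widened by 14 days.

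**Size, part (a).** Inputs from the documents: 45 perinatal deaths per 1,000 deliveries (protocol 3.2, SAP 6.2) and 5,483 evaluable women per arm. Assumed, because the documents do not give them: 40–60% of perinatal deaths are stillbirths, 20–60% of stillbirths are macerated, and aspirin changes macerated deaths only, by 30%.

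- Perinatal deaths per arm: 0.045 × 5,483 = 246.7.
- Omitted by the row, low: 246.7 × 0.4 × 0.2 = 19.7 (8% of perinatal deaths).
- Omitted by the row, high: 246.7 × 0.6 × 0.6 = 88.8 (36%).

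With macerated share m, the risk ratio for stillbirth as the protocol defines it is 1 − 0.3m for benefit or 1 + 0.3m for harm. In the SAP row the counted events are the same in both arms and only the denominators differ. Its risk ratio is therefore (n − M)/(n − M × RRm), where n = 5,483, M is the number of macerated deaths in the placebo arm and RRm is 0.7 or 1.3.

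| Scenario | Protocol outcome, m = 0.2 to 0.6 | SAP row, M = 19.7 to 88.8 |
|---|---|---|
| Macerated deaths cut by 30% | 0.94 to 0.82 | 0.999 to 0.995 |
| Macerated deaths raised by 30% | 1.06 to 1.18 | 1.001 to 1.005 |

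For example, with M = 88.8 and RRm = 0.7: (5,483 − 88.8)/(5,483 − 62.2) = 5,394.2/5,420.8 = 0.995.

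**Size, part (b).** Assume 1 to 5 deaths per 1,000 between 20 weeks 0 days and 21 weeks 6 days; the documents give no rate.

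- 0.001 × 5,483 = 5.5 and 0.005 × 5,483 = 27.4 deaths per arm.
- Against 246.7 this is 2.2% to 11.1%, if the registry figure of 45 per 1,000 counts from 22 weeks. The documents do not state the registry's threshold.

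**The case against.** The case for leaving this as a minor tidy-up is reasonable.

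- **Status.** SAP 7.5 allows one formal test, on preterm birth, and treats secondary outcomes as exploratory. SAP 9.6 uses stillbirth only for estimation and hypothesis generation. This stands and limits the severity.
- **Openness.** The exclusion and the 20-week threshold are both written in the SAP. This also stands: nothing is hidden. What is missing is the label and, for perinatal mortality, the Section 12 entry.
- **Coverage elsewhere.** Perinatal mortality counts macerated stillbirths, fetal loss counts deaths from 16 weeks, and Table 6 gives a relative risk for fetal loss after 20 weeks. The trial as a whole would therefore not miss an effect. Table 6 is a weaker substitute, because it rests on serious adverse event reports in the safety population.
- **Little bias.** At most 88.8/5,483 = 1.6% of infants leave the denominator, which moves the row's risk ratio by about 0.005. This is correct. The fault is that the row estimates a different outcome under the protocol's name.
- **Reclassified miscarriages.** Unknown maceration counts as Yes, so an uncoded case has a default. That answers part of the point. How a coded case is handled is still unstated.
- **Harmonisation.** Protocol 3.1.2 already analyses secondary outcomes among deliveries after 20 weeks. That fixes who is analysed. It does not alter the 22-week event definition in Appendix 3.
- **Assumed magnitudes.** The shares, the 30% effect and the rate at 20–21 weeks are assumptions, and an effect on macerated deaths alone is an extreme case. If the registry already counts from 20 weeks, the 2–11% is not an addition to 247. The figures are illustrations only.

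**Conclusion.** The concern holds. As written, the stillbirth row would give a risk ratio that does not estimate the protocol's outcome, and stillbirths plus early neonatal deaths would not add up to perinatal mortality. The perinatal-mortality row contradicts itself by 14 days and changes a named secondary outcome without declaring it.

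These conclusions come from the text and from 20 × 7 = 140; they need no assumption. The scale does. Under the assumed shares, 20 to 89 deaths per arm drop out of the stillbirth row, and an effect that would show as 0.82 on the protocol's outcome could show as 0.995. For the threshold, the assumed rates put 5 to 27 deaths per arm in the disputed two weeks.

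The primary outcome and the only formal test are untouched. This should be fixed, but it does not threaten the trial's main result.

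**What to change.** 1. In SAP 9.2, count every stillbirth at or after 20 0/7 weeks: fresh, macerated, unknown and reclassified miscarriage. Show fresh and macerated cases as sub-rows.
2. If the exclusion is kept, rename the row as non-macerated stillbirth, mark it as a departure from the protocol, and state how maceration is handled for reclassified miscarriages.
3. In the perinatal-mortality row, change 154 days to 140 days.
4. List the move from 22 to 20 weeks in SAP Section 12, and report perinatal mortality from 22 weeks as a sensitivity row.

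Item 1 (or 2), item 3 and the Section 12 entry are enough to resolve the inconsistency. The sub-rows and the 22-week row are inexpensive additions that let readers compare with the protocol. The SAP already takes maceration status from the registry forms and gestational age from the study forms, so the cost is wording and a few table rows. The changes should be made before unmasking.

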## 9.4 Primary Analysis

The primary analysis will compare the risk of preterm birth between the two treatment arms using two complementary approaches. First, the formal test of the primary hypothesis that the risk of preterm birth differs between the two arms will utilize a modified intention-to-treat approach based on a Cochran-Mantel-Haenszel test stratified by Global Network sites. The approach is characterized as a modified intention to treat approach because the analysis population for the test will be all randomized pregnancies for which the delivery occurs after 20 weeks. Earlier deliveries (miscarriages) will be considered missing completely at random for purposes of this analysis.

In order to evaluate the sensitivity of the primary hypothesis test to the assumption by which miscarriages are treated as randomly missing and to control for potential confounders of the treatment effect, additional analyses will be conducted using a series of three generalized linear models. These generalized linear models will be fit with the binary outcome of preterm (<37-week delivery) as the outcome measure. The initial model will include terms for treatment, site, and a treatment by site interaction. If the treatment by site interaction term is found to be significant ( $p<0.05$ ), then all subsequent models will include the interaction term and all effects will also be reported by site, although formal inference will be based on the average effect across sites. If the interaction term is not significant, it will be removed from the model and this initial model be used to estimate an unadjusted treatment effect controlling for site. The second series of models will include any demographic or clinical variable found to differ significantly between the treatment arms in the preliminary analyses described above. These models will be used to generate adjusted estimates of the treatment effect controlling for potential confounders. The third set of models will utilize extensions of the generalized linear model that incorporate inverse probability weighting to evaluate the sensitivity of the inference to treatment of miscarriages as randomly missing (Hogan, 2004). As described in Section 7.3, we will also conduct sensitivity analyses using the full ITT population; for these analyses, missing data due to loss to follow-up will be handled using multiple imputation, and these early terminations will be treated as preterm deliveries.

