## **7.4 Multicenter Studies**

For this multicenter study, randomization of study participants was stratified within site. Consequently, for all test-based analyses of treatment effect and model-based primary and secondary analyses, site will be included as a fixed effect in the models. As an ancillary analysis associated with the primary outcome (risk of premature delivery) as well as secondary outcomes, we will examine

descriptively whether the treatment effects vary across sites; however, these analyses of site differences in treatment effect are considered to be descriptive because sample sizes are likely inadequate to provide adequate power to detect site by treatment interaction effects.

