## **7.5 Multiple Comparisons and Multiplicity**

There is only one formal hypothesis test for this study. As such, a statistical test will be conducted at a 5% type I error rate (two-sided) for the primary efficacy measure, and no adjustments for multiplicity will be made. All analyses of secondary outcomes are exploratory in nature; therefore, p-values and confidence intervals are provided for descriptive purposes only. All p-values provided for any baseline and demographic characteristics and safety parameters will be for descriptive purposes only. As such, unless otherwise specified, p-values presented will be on a per analysis basis, with no further control for multiple tests.

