## 9.5 Secondary Outcome Analyses

This study has been designed to evaluate the differences between the two treatment arms for three secondary outcomes: the risk of perinatal mortality; the risk of eclampsia/preeclampsia, and the risk of a SGA delivery. As with the primary analyses, each of these outcomes will be examined individually using descriptive tests of hypotheses that the risk differs between the two arms based on Cochran-Mantel-Haenszel tests stratified by Global Network sites. The analyses for each of these 3 secondary outcomes will utilize the same modified intention-to-treat population used for the primary outcome. Each of these hypothesis tests will be conducted at the 0.05 level of significance with no adjustment for multiple comparisons. In addition to this set of hypothesis tests, model-based analyses comparable to those conducted for the primary analyses will be used to evaluate potential heterogeneity of treatment effect across sites and evaluate potential confounding. For each of the 3 outcomes, an initial model will include terms for treatment, site, and a treatment by site interaction. If the treatment by site interaction term is found to be significant ( $p<0.05$ ), then all subsequent models will include the interaction term and all effects will be reported by site; because the study will lack power to detect site-specific effects, all p-values will be reported for the average effect and site effects will include point and interval estimates. If the interaction term is not significant, it will be removed from the model and this initial model be used to estimate an unadjusted treatment effect controlling for site. The second series of models will include any demographic or clinical variable found to differ significantly between the treatment arms in the preliminary analyses described above. These models

will be used to generate adjusted estimates of the treatment effect controlling for potential confounders.

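### SAP 9.4 and 9.5 let a site-interaction pre-test at p<0.05 choose the model behind the reported effect estimates, and the across-site average used when it is positive is undefined

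*Combined protocol and SAP*

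**What the plan says.** SAP 9.4 first names the formal test without any condition: "the formal test of the primary hypothesis that the risk of preterm birth differs between the two arms will utilize a modified intention-to-treat approach", using a CMH test stratified by site. SAP 7.5 agrees: "There is only one formal hypothesis test for this study", and "a statistical test will be conducted at a 5% type I error rate (two-sided) for the primary efficacy measure".

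The next paragraph of 9.4 adds supporting models: "additional analyses will be conducted using a series of three generalized linear models". The first contains treatment, site and their interaction. If the interaction has p<0.05, the rule is: "then all subsequent models will include the interaction term and all effects will also be reported by site". For that branch the SAP attaches a qualifier: "although formal inference will be based on the average effect across sites". Without significance, the interaction is removed and the model gives one site-adjusted effect. The covariate-adjusted and inverse-probability-weighted (IPW) models follow the same branch.

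SAP 9.5 repeats the rule for the three secondary outcomes (unadjusted and adjusted models only). On the positive branch, "all p-values will be reported for the average effect and site effects will include point and interval estimates". The same section assigns those outcomes CMH tests.

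SAP 7.4 calls the examination of site differences descriptive, because "sample sizes are likely inadequate to provide adequate power to detect site by treatment interaction effects".

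The Table 5a note takes its p-value from the CMH test. Table 5b gives site RRs from an interaction model, with the interaction p-value, whatever the pre-test shows.

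**The concern.** A test that the SAP itself regards as weak decides which model produces the RR. The quantity estimated then depends on the data: a common RR on one branch, and an average of site effects with unstated weights and scale on the other. A frequent software default averages the site log-RRs equally, so a small, low-risk site counts as much as the largest. The RR printed beside the CMH p-value could then disagree with it or be much less precise. The adjusted and IPW analyses, which are meant to check the primary result, would carry the same problem.

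The phrase about formal inference sits in the supporting-model paragraph, although 9.4 and 7.5 have already placed formal inference on the CMH test. Two statements of where inference rests invite a dispute if they disagree.

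**Working it through.** **Inputs from the SAP.** Risks of 8% and 6.4%, 90% power, 5,483 evaluable and 5,960 randomized per arm, and site preterm rates of 2.9% to 9.8% (6.1); two-sided 5% (7.5); seven sites, none above 25% of the total (4.3).

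**Assumptions.** RR 0.80 at every site. Seven evenly spaced site risks from 2.9% to 9.8%, rescaled so that the overall control risk is 8%, in every assignment to sites. Three site-size layouts, shown below.

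**1. The plan's own figure.** n = [1.960·√(2·0.072·0.928) + 1.2816·√(0.08·0.92 + 0.064·0.936)]² / 0.016² = (0.7165 + 0.4683)² / 0.000256 ≈ 5,483. Then 5,483/0.92 = 5,960. Both match.

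**2. Precision of the two kinds of average.** For site i with share sᵢ, nᵢ = 5,483·sᵢ per arm, control risk pᵢ and qᵢ = 0.8pᵢ:

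- vᵢ = (1−pᵢ)/(nᵢpᵢ) + (1−qᵢ)/(nᵢqᵢ)
- common RR: SE = 1/√Σ(1/vᵢ)
- equal-site average: SE = √(Σvᵢ)/7
- size-weighted average: SE = √Σ(sᵢ²vᵢ)
- power = Φ(|ln 0.8|/SE − 1.96), with |ln 0.8| = 0.2231

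Worst case, sizes 25/25/20/12/8/6/4% with risks falling from 10.25% in the largest site to 3.03% in the smallest: Σ(1/vᵢ) = 211.0 and Σvᵢ = 0.678.

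- Common RR: SE 0.0688, power Φ(1.28) = 90%.
- Equal-site average: SE √0.678/7 = 0.1177, 1.7 times as large; power Φ(−0.06) = 47%.

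| Site sizes (%) | Common RR | Equal-site average | Size-weighted average |
|---|---|---|---|
| seven equal | 90% | 84% | 84% |
| 25/20/15/12/12/9/7 | 90% | 65%-90% | 82%-86% |
| 25/25/20/12/8/6/4 | 90% | 47%-88% | 81%-87% |

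With 8% risk at every site, equal sites lose nothing; the two unequal layouts give 85% and 74% for the equal-site average.

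These are powers of each estimator if it is used. They do not include the chance that the branch is entered.

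**3. How often the branch is entered.** This used a 6-df heterogeneity test on site log-RRs at 5,483 per arm, over five assumed combinations of site sizes and rates. With no heterogeneity it is positive in about 4%-5% of trials. Its power is 14%-21% for site RRs of 0.7 versus 0.9, 50%-75% for 0.6 versus 1.0, and 89%-99% for 0.5 versus 1.1. So it usually misses modest heterogeneity, as SAP 7.4 expects.

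**4. Error rates, by simulation over the same five combinations.** CMH alone: type I error 0.049-0.051. A literal switch to the equal-site average after a positive pre-test: 0.050-0.054. Under the null, among trials with a positive pre-test, the two tests disagreed on significance in 1%-16%.

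**5. Under real heterogeneity.** With site RRs alternating 0.6 and 1.0 (0.8 at the seventh), the literal switch gave 94% power against 90% for CMH with equal sites at 8% risk. It gave 66% against 97% with sizes 25/25/20/10/10/5/5% and the lowest rates in the smallest sites. The direction depends on the layout because the two averages are different quantities.

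**The case against.** **A reader might infer that a significant interaction moves formal inference off the CMH test.** The documents do not support this. SAP 9.4 names the CMH test as the formal test with no condition, 7.5 allows one formal test, and the Table 5a note takes its p-value from CMH. The pre-test belongs to models described as additional. Protocol 3.1.1 has the same pre-test without the average-effect clause, so the clause reads naturally as a safeguard against splitting the overall conclusion by site. This objection stands; what remains is ambiguous wording.

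**A reader might also take 90% against 47% as the power the trial loses.** It is not. With homogeneous effects the branch is entered in about 5% of trials. If its entry is treated as independent of the estimate, the average loss in the worst layout is about 0.05 × (90 − 47) ≈ 2 percentage points. That loss falls on a supporting model.

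**The severe figures depend on assumptions.** Equal weighting is one reading, and size weighting is as natural. Site sizes and the pairing of low risk with small sites are not in the documents. Rescaling to 8% lifts some site risks in other assignments as high as 15.5%, above the plan's 9.8%. This stands, and the range is wide because the SAP leaves the average undefined.

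**Some of the exposure is already limited.** An overall effect is reported on both branches, site results appear in Table 5b regardless, adjusted RRs are not planned for the primary paper, and 7.5 treats secondary p-values as descriptive. All true, but the unadjusted RR in Table 5a and the IPW check still depend on the branch.

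**Conclusion.** The concern holds for the supporting models. A pre-test that the SAP regards as likely underpowered selects the model behind the unadjusted and adjusted estimates and, for the primary outcome, the IPW estimate. One branch uses an average that neither document defines. This conflicts with the descriptive status that SAP 7.4 gives to site differences.

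The CMH test remains the only formal test, and the planned size of 5,483 per arm stands. Even a literal switch would bring type I error to no more than about 0.054 in the combinations examined, so this is not a problem of error control. The consequence is a possible mismatch between RR and p-value, and a loss of precision when the branch is entered. How large that loss is depends on the assumed layouts and on weights that the SAP does not state. The change is worth making because it is cheap and gives up nothing.

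**What to change.** - Delete the p<0.05 interaction test as a model-selection rule in SAP 9.4 and 9.5, and in the analogous models of 9.6.
- State that the site-stratified CMH test is the only formal test of the primary hypothesis whatever the interaction result, and that Table 5a p-values come from CMH tests.
- Always report the common RR from the treatment-plus-site model in Table 5a, and build the adjusted and IPW models on it.
- Fit the interaction model separately for Table 5b, with its p-value and the site RRs labelled descriptive, in line with 7.4.
- Remove the formal-inference clause from 9.4 and the matching p-value clause from 9.5.
- List the change in SAP section 12, since Protocol 3.1.1 and 3.1.2 contain the pre-test.

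The cost is SAP wording only, to be settled before the unmasking that SAP 4.4 places after data lock. Sample size and data collection do not change, and Table 5b already carries the site RRs and the interaction p-value.
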